Two knee arthroplasty surgeons (SJM, DBC) at one hospital will perform all surgeries. Each surgeon will assess compartmental loads at three positions of knee flexion, verified by navigation data, and these measures will be repeated by the surgical assistant to ensure inter-observer reliability and consistency. The surgical technique described in Appendix 2 and 3. Data will be collected on the frequency and degree of any further adjustments required to satisfactorily balance the knee, as well as the final balance achieved. Although the surgeons will not be blinded to the allocation, the participants, assessors and statisticians will be blinded to enable unbiased collection of patient-reported outcomes and functional outcomes as secondary outcome measures.

To maintain the integrity of the trial, unblinding will occur only when knowledge of the alignment allocation is essential for further clinical management of the patient. Because both treatment arms offer current, routine standards of care, we do not anticipate this need will eventuate. If necessary however, the investigator will contact

the study coordinator to obtain the allocation assignment, and the code break will be reported in the context of Complications documentation.

Inclusion criteria

1. Patients who meet the indications for primary unilateral or bilateral total knee arthroplasty using the Smith & Nephew Legion™ posterior-stabilised total knee arthroplasty system.
2. Patients diagnosed with one or more of the following conditions:
 - Osteoarthritis
 - Rheumatoid inflammatory arthritis
 - Post-traumatic osteoarthritis

Exclusion criteria

1. Revision TKA
2. Previous insufficiency fracture
3. Prior Grade 3 ligamentous knee injury to posterolateral corner (PLC) or lateral collateral ligament (LCL). Grade 3 medial collateral ligament (MCL) injuries treated conservatively may be included so long as they were deemed by the surgeon to have healed with a maximum of Grade 1 laxity.
4. Prior femoral, tibial or patellofemoral osteotomies
5. Ipsilateral foot/ankle or hip arthritis
6. Patients who are unable to provide consent or fulfil the study requirements due to cognitive incapacity or English-language deficiency

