Trial components will then be inserted prior to any soft tissue release (other than those required by a standard approach). During trialling, the surgeon will determine the most suitable size of tibial insert, and this will be replaced by a VERASENSE™ insert of the same size. The extensor mechanism will be approximated using a towel clip, and the knee cycled through a full range of movement. Occasionally it may be necessary to change the thickness of the VERASENSE™ insert in response to the pressures being either too high or too low. In this case, the data recordings will be repeated, and the new values will replace those recorded initially. Assessment of knee extension with the computer navigation system will be performed concurrently to ensure that an extension loss of no more than 5 degrees is apparent.

Following this, the surgeon will support the posterior thigh with one hand and rest the heel in the other to reduce the amount of varus and valgus stress placed on the knee (Appendix 1). The knee will then be flexed to 90 degrees (using the optical navigation

to quantify the flexion) and the pressure values captured in this position. This will be repeated at 45 degrees and 10 degrees. The readings will be recorded on the study data collection form by a non-operative member of the surgical team. These steps will be repeated by the surgical assistant, and the data recorded for a second time.

The surgeon will then undertake final balancing of the total knee replacement by standard operating techniques using the Verasense™ insert (Appendices 2 and 3). Any soft tissue or bony adjustments undertaken to achieve this will be recorded on the data collection form. Once knee balancing has been performed, the pressure data will be recorded again.

INTERVENTIONS

Intervention (KA) Group

In the KA group, the surgeon will perform the initial bony resections according to the surgical plan that was defined prior to randomisation. This plan will include an aim for femoral and tibial component position relative to the mechanical axis of the bones. These resections will be guided and validated by the computer navigation system to ensure maximum accuracy. The rest of the procedure will be completed as per the surgical technique described above.

Control (MA) Group

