The surgeon will perform the initial bony resections using the same computer navigation system aiming for tibial and femoral component position perpendicular to the mechanical axis of the bone and an overall HKA of 0 degrees. These resections will be validated using the same computer navigation equipment to ensure maximum accuracy. The rest of the procedure will be completed as per the surgical technique described above.

OUTCOME MEASURES

Baseline Measures

Demographics

Baseline demographics will include age at time of surgery, gender, side of surgery, height, weight, body mass index, and primary diagnosis (osteoarthritis, rheumatoid arthritis, post-traumatic osteoarthritis).

Pre-operative Radiographic Data

Radiographic data to be recorded before surgery will include:

1. Hip-knee-ankle (HKA) angle. This is the angle subtended by the mechanical axis of the femur and mechanical axis of the tibia, with a negative value used for varus alignment and positive value for valgus alignment.
2. Lateral distal femoral angle (LDFA). This is the lateral angle subtended by the mechanical axis of the femur and a line across the distal femoral articular surface.
3. Medial proximal tibial angle (MPTA). This is the medial angle subtended by the mechanical axis of the tibia and a line across the proximal tibial articular surface.

Operative Data

Operative data to be recorded will include size of femoral component, size of tibial component, thickness of tibial bearing, size and type (oval, round onlay, inset) of patellar component, total operating time from wound incision to skin closure, intra-operative complications, VERASENSE™ data at 90, 45 and 10 degrees, and any soft tissue or bony adjustments made after the VERASENSE™ recordings.

In-Hospital Data

In-hospital data to be obtained will include total length of stay (from day of surgery to day of discharge), and discharge destination (home, in-patient rehabilitation unit, nursing home facility). Other data to be collected will include blood transfusion requirement (total number of units administered) and other in-hospital complications as specified in Table 2.

Primary Outcome Measure

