The primary outcome measure of this study will be the initial difference in pressure between the medial and lateral compartments at 10 degrees of flexion (10-degree pressure delta). Because the compartment pressures will be assessed by both the operating surgeon and an assistant, the mean difference of the two readings will constitute the primary outcome measure.

Secondary Outcome Measures

Knee-Specific Outcome Scores

- *Knee injury and Osteoarthritis Outcome Score (KOOS - www.koos.nu)* - The KOOS score is a patient-administered instrument widely used to assess patients' opinions about their knee pain and function. It consists of five

subscales: Pain, other Symptoms, Activities of Daily Living (ADL), Sport and Recreation (Sport/Rec) and knee-related Quality of Life (QOL). A normalised score is calculated for each subscale, with 100 indicating no symptoms and 0 indicating extreme symptoms. The minimum clinically important change in KOOS has been defined as 8-10 points on a 100-point scale with a reported standard deviation of 16 [28, 29]. We will use the mean of the 3 subscale scores - KOOS Pain, KOOS Symptoms and KOOS ADL with the primary outcome end point will be change in the mean KOOS from pre-operative scores and 12 months. The KOOS at six months, two years, five years and 10 years will also be recorded. We will also analyse each of the five subscale separately as secondary endpoints.

- *Forgotten Joint Score - Knee (FJS-12 Knee - <http://www.forgotten-joint-score.info/knee>)* - The FJS-12 is a patient-reported tool that was designed to assess patient outcome in patients undergoing conservative or operative treatment of the knee, and focuses on patients' awareness of their knee in everyday life. Joint awareness can be defined as any unintended perception of a joint. This may include strong sensations like pain, but also includes more subtle feelings like mild stiffness, subjective dysfunction, or any discomfort. Generally, joint awareness comes with a negative connotation as healthy joints do not cause 'awareness' in daily life – and are essentially 'forgotten'. The FJS-12 Knee has low ceiling effects, allowing monitoring of longer term outcomes, particularly in well-performing groups after total joint arthroplasty [30]. The FJS-12 will be measured pre-operatively and at one year and two years post-operatively.

Quality of Life Measures

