For the secondary outcome measures, however, strategies for improving adherence to protocol include clear elucidation during the consenting process of the importance of committing to the schedule of follow-up visits, PROMs, and x-rays. Participants will have an opportunity to ask questions, and key messages about the study will be reinforced, at each follow-up visit. In order to prevent missing data and avoid associated complexities in study analysis and interpretation, administrative systems will be employed to diligently schedule follow-up appointments, provide reminders and monitor retention. It is projected that the rate of loss to follow-up for the secondary objectives will be no more than 5%.

Complications

Complications to be recorded will include intra-operative complications, Serious Adverse Events related to the index operation and Adverse Events unrelated to the operation, as defined by the ACORN registry (Table 1). Post-operative complications will be assessed and recorded at all follow-up time points (Table 3), and as necessary at unscheduled times.

Patient-reported outcomes will be monitored throughout the study to supplementally inform the clinical care of individual participants, but their timing coincides with scheduled clinical assessment in any case.

Radiographic Measures

Radiographic investigation will be defined by CT Perth Protocol [31, 32]. This will include HKA Angle, LDFA and MPTA, as well as femoral and tibial component sagittal and rotational position. A routine series of radiographs (AP erect, lateral and skyline views) will also be performed pre-operatively, at six months and two years.

Intra-operative Outcome Measures

Tibiofemoral Compartmental Pressure Loads - Initial medial and lateral compartmental pressure and final medial and lateral pressure loads will be

compared in both groups at 10°, 45° and 90° of knee flexion. Optimal knee balance will be defined as a pressure difference of less than 15 lb between compartments at 10°, 45° and 90° of knee flexion, with no pressure exceeding 40 lbs.

Functional Outcome Measures

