The primary outcome measure (initial pressure delta between medial and lateral compartments at 10 degrees of flexion) will be recorded intra-operatively by operating room staff in a locked and password-protected spreadsheet. The surgeon and assistant surgeon will each confirm the recorded measurement at the end of each case, and longitudinal checks for consistency and validity will be employed throughout the study.

All PROM data will be obtained from patients at pre-operative and post-operative consultations in paper form, and then stored centrally in a locked and password-protected electronic database (Socrates). Intra-operative data will be collected by members of the surgical team. In-hospital data will be collected by the trial coordinator. A CT radiographer with experience in performing post-operative alignment measures will be blinded to patient allocation, and will perform all CT-based radiographic measures.

No formal data monitoring committee is deemed necessary for this trial because of its minimal risks and because both trial arms offer standard, accepted surgical interventions. The accumulating data, however, will be monitored continuously by the principal investigator and the study monitor to determine if the trial should be modified or discontinued.

Auditing of trial conduct, including site monitoring visits, will be carried out independently by the Bellberry Limited Human Research Ethics Committee.

Stopping Rules

The trial will be terminated early if there are two (2) or more cases of tibiofemoral knee joint instability, patellofemoral instability or implant subsidence or loosening in patients assigned to the intervention arm within two years post-operatively, or if monitoring indicates a pattern of unexpected serious adverse events.

DATA ANALYSIS

The primary outcome for this study will be soft tissue balance, defined as the mean of the initial difference in pressure between the medial and lateral compartments at 10 degrees of flexion (10-degree pressure delta) measured by both the surgeon and the assistant intra-operatively immediately after the bone cuts and prior to any soft tissue correction.

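### Unblinded surgeons may swap the sensor insert on the loads they see, with no numeric trigger; the retaken reading then replaces the first in the primary outcome, and no data item records the swap

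*Protocol*

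**What the plan says.** The Protocol's Primary Outcome Measure section defines the endpoint as "the initial difference in pressure between the medial and lateral compartments at 10 degrees of flexion", averaged over the surgeon's and the assistant's readings. Data Analysis places it "immediately after the bone cuts and prior to any soft tissue correction".

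Surgical Technique sets the order of events. "During trialling, the surgeon will determine the most suitable size of tibial insert", and a sensor of that size goes in. The surgeon may then occasionally change the thickness of the sensor "insert in response to the pressures being either too high or too low". When that happens, "the data recordings will be repeated, and the new values will replace those recorded initially".

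On blinding, Study Design begins its statement with "Although the surgeons will not be blinded to the allocation". Allocation has the envelope opened just before anaesthesia, so the arm is known before any sensor reading exists.

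On recording, Operative Data lists the sensor readings, the thickness of the tibial bearing, and "any soft tissue or bony adjustments made after the" sensor recordings. It lists neither a change of sensor insert nor the readings that were replaced.

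**The concern.** The loads that prompt a change of insert are the loads whose difference is the primary outcome. The person deciding knows the allocation, and no number at this step limits the decision. If surgeons are readier to change the insert in one arm than in the other, the contrast between arms contains a component that comes from that behaviour and not from the alignment method. If they behave identically, the arm with more extreme loads will still have more of its readings retaken.

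The initial-load comparison listed under Intra-operative Outcome Measures is exposed in the same way. Averaging two readers does not protect against this, because the assistant reads the insert that the surgeon has chosen. A statistical analysis plan could not repair it either: a replaced reading that was not kept is not there to analyse.

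**Working it through.** **1. Is there a numeric trigger elsewhere that governs this step?** There are two candidates, and neither does.

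- The definition of optimal balance under Intra-operative Outcome Measures ends "with no pressure exceeding 40 lbs". That describes a balanced knee; it does not say when to change an insert.
- The manufacturer's balancing guide in the Appendices advises a thicker shim for loads under 10 lb, under its flexion-gap heading. That is balancing advice and is not tied to the trialling step. It does show that a thickness change is regarded as a corrective action.

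**2. Does the rule contradict the endpoint definition?** No. Data Analysis requires the reading to come after the bone cuts and before soft tissue correction. An insert change releases no tissue and recuts no bone.

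**3. Is a trace kept?** Study Design promises data on the frequency and degree of further adjustments needed to balance the knee, which might be read to include insert changes. Operative Data records bearing thickness, which does not show that an insert was changed or what the loads were before. Neither item preserves the first reading.

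**4. The plan's own figure.** Inputs from Sample Size: difference 15, SD 30, power 80%, 5% significance (two-sided assumed). Allocation is 1:1.

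n per arm = 2 × (1.960 + 0.842)² × 30² / 15² = 62.8, so 63 per arm and 126 in total. The stated 125 reproduces. The point does not dispute it.

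**5. What differential retaking could do (assumption only).** Suppose an excess share f of one arm is retaken and each retake lowers the difference by d psi. The spurious shift is b = f × d. The standard error of the arm difference at 62.5 per arm is 30 × √(2/62.5) = 5.37. With no true effect, the two-sided type I error is Φ(−1.96 + b/5.37) + Φ(−1.96 − b/5.37). If the excess is in the control arm, power for a true 15 psi difference is Φ((15 − b)/5.37 − 1.96), which is 79.8% at b = 0.

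| f (knees of 62.5) | d | b | Type I error | Power |
|---|---|---|---|---|
| 5% (about 3) | 5 | 0.25 | 5.0% | 78.5% |
| 10% (about 6) | 10 | 1 | 5.4% | 74.2% |
| 20% (12.5) | 10 | 2 | 6.6% | 67.8% |
| 20% (12.5) | 20 | 4 | 11.6% | 53.6% |

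Neither f nor d is in the documents. Shrinkage itself is assumed: a thickness change acts on both compartments, so it could raise the difference. The table shows only that the effect is trivial at a small imbalance and matters at a large one.

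**The case against.** The case on the other side is substantial.

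- **The rule may simply finish insert selection.** It is stated before the formal capture at 90, 45 and 10 degrees, applies to both arms, and precedes any release. A reader might infer that it contradicts the endpoint definition; as shown above, it does not. But the text says that readings are repeated and replaced, so values exist when the decision is made.
- **Changes are expected only occasionally.** This stands. At a rare, balanced rate the effect is negligible. No rate is given, however, and since changes are not listed for recording, rarity could not be shown afterwards.
- **The first reading is not obviously the better one.** This also stands. On an insert that is too thin, both loads may be near zero and a loose knee would look balanced. The first insert is itself chosen by an unblinded surgeon. A reader might infer that the first reading must become primary; the documents do not support that.
- **Some safeguards exist.** Data Collection and Monitoring has surgeon and assistant confirm the recorded measurement, with consistency checks over time. Also, replacing a value need not mean destroying the first entry. So it is too strong to say that nothing could ever be checked. But nothing in the Protocol requires the first value to be kept.

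**Conclusion.** The point holds as a weakness in how the primary outcome is fixed. For knees whose insert is changed, the primary value is retaken after a decision that is load-driven, made with knowledge of the arm, and not bound by a number. Differential use would bias the contrast between arms and could not be reliably checked from the data listed for collection.

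The size is not determinable from the documents. The shifts of 0.25 to 4 psi in the table (1.7% to 27% of the 15 psi target: 0.25/15 and 4/15) rest wholly on assumed retake rates and effects. An excess of 20% would be hard to square with changes being occasional. A reader might infer that the trial's primary result is biased, that its type I error is inflated by a known amount, or that retaking always pulls the contrast toward zero. None of these is supported, because neither the frequency of a change nor the direction of its effect is stated. The sample size is unaffected.

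**What to change.** 1. In Surgical Technique, state one numeric trigger for an insert change, identical in both arms and tied to named flexion angles. One option uses limits already in the Protocol: any compartment above 40 lb, or both below 10 lb. The choice of limits is clinical.
2. Keep both sets of readings, and record each insert change on the data collection form.
3. Report the share of knees changed, by arm.
4. Prespecify a sensitivity analysis of the primary outcome using the first readings in place of the replacements.

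Which reading is primary may stay as the Protocol has it. The cost is one sentence in Surgical Technique and one extra line on the form. Where the rule applies, the first readings have already been taken, so no further measurement is needed.

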Knee Range of Motion – The patient's range of motion will be measured by a blinded orthopaedic nurse at two weeks, eight to twelve weeks and one year post-operatively. Two photographs will be taken with the patient in the supine position with markers placed on the greater trochanter, lateral epicondyle of the femur and lateral malleolus. One photograph will be taken in maximal active extension and one in maximal active flexion, with the nurse standing between 1 and 1.2m from the table to get the entire lower limb in full view and holding the camera lens level with and parallel to the patient's knee. Measurements from the photographs will be taken using computer angle measurement software. Knee flexion will be recorded as a positive value and knee hyperextension as a negative value. The following will be recorded: maximal active extension (with hyperextension as negative, full extension as zero and flexion contracture as positive); and maximal active flexion. From these two values, the arc of knee motion will be recorded (flexion minus extension).

SAMPLE SIZE

The senior authors have previously recorded the initial and final intra-compartment pressures of 280 consecutive TKAs using the VERASENSE™ device. The mean initial 10-degree pressure difference was 30psi (SD 30psi). The manufacturers recommend a pressure difference between lateral and medial compartments of <15psi in order for the knee to be balanced. Using a 5% significance, a standard deviation of 30 and an 80% power to detect a difference of 15psi, a sample size of 125 will be required. As the primary outcome measure is an intraoperative measurement, loss to follow-up will not be significant.

In addition, we aim to determine whether any differences exist in patient reported outcomes in balanced TKA's inserted with the KA or MA method. Roos and colleagues in 2003 reported a change in KOOS Pain, KOOS Symptoms and KOOS Function of 45, 37 and 41 a cohort of patients undergoing TKA [28]. The minimal clinically important change in KOOS was between 8 and 10, with a standard deviation of 16. Using a one-to-one allocation, 5% significance and 80% power to detect a 8 point change on KOOS score, a sample size of approximately 64 patients per group will be required, which would approximate the sample size of our study. [Table 2].

DATA COLLECTION AND MONITORING

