The aggregate, de-identified results of this research will be presented at both national and international orthopaedic surgical meetings such as the Australian Orthopaedic Association Annual Scientific Meeting, the Australian Knee Society Meeting, and the American Academy of Orthopaedic Surgeons. We aim to have this research submitted to a high-impact medical or surgical journal for publication, and all investigators are eligible for authorship in such publications.

It is also anticipated that the results of this trial will inform future research efforts, clinical practice and surgical guidelines internationally. To that end, and to enhance transparency, reproducibility and interpretation of the study results, this protocol will be made publicly available via open-access digital publication. Additionally, the authors will publish a de-identified, participant-level data set and statistical code after journal publication to enable verification and replication of the study.

TABLES

Table 1. Adverse Events (as per ACORN Protocol)

- Drug Reaction
- Delirium
- SSI requiring oral antibiotics
- SSI requiring IV antibiotics
- SSI requiring surgery without prosthetic removal
- SSI requiring surgery with prosthetic removal
- Deep venous thrombosis
- Pulmonary Embolus
- Fat Emboli
- Respiratory Infection
- CVS
- Dislocation
- Fracture
- Nerve Injury
- Urinary Tract Infection
- Urinary Retention
- Wound Dehiscence
- Reoperation During Index Admission
- Pressure Area
- Fall
- Hypotension
- Cellulitis
- Death
- Other

Table 2. Sample Size Calculation

Parameters	Results
Power	80%
Alpha	0.05
Mean (Group 1)	30
Mean (Group 2)	15
Standard deviation	30
Sample size	125
Power (obtained)	1

Table 3. Schedule of Study Assessments

	Pre-op	Intra-op	On discharge	2 weeks	6-8 weeks	6 months	1 year	2 years
Written informed consent	X							
Demographics	X							
VERASENSE™ Data		X	X					
KOOS	X					X	X	X
FJS	X						X	X
EQ5D-5L, Satisfaction	X					X		X
Knee Range of Motion	X			X	X	X		
Radiographs	X		X			X		X
CT Perth Protocol			X					
Adverse Event Reporting		X	X	X	X	X	X	X

Table 4. SPIRIT 2013 Checklist with SPIRIT-PRO Extensions

SPIRIT 2013 Checklist with SPIRIT-PRO Extensions				
SPIRIT Section	Item No.	Item Description	SPIRIT-Pro Extension	Addressed on Page No.
Administrative Information				
Title	1	Descriptive title identifying study design, population, interventions, and if applicable, trial acronym		Title page

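### Table 2 gives an obtained power of 1 for 125 patients where the design delivers about 0.79, and the KOOS power figure leaves out the protocol's own projected loss

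*Protocol*

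**What the plan says.** **Primary outcome.** The Sample Size section draws on an earlier series of 280 knees: "The mean initial 10-degree pressure difference was 30psi (SD 30psi"). At 5% significance it concludes: "80% power to detect a difference of 15psi, a sample size of 125 will be required".

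**Table 2 (Sample Size Calculation).** The table lists power 80%, alpha 0.05, group means 30 and 15, standard deviation 30 and sample size 125. Its last row, which begins "Power (obtained", carries the value 1.

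**KOOS.** With one-to-one allocation, 5% significance, 80% power, a difference of 8 points and SD 16, the same section states: "a sample size of approximately 64 patients per group will be required, which would approximate the sample size of our study". It then points to Table 2, which holds only the pressure inputs. No allowance for loss is added.

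**Loss and capacity.** Under Secondary Outcome Measures the protocol projects that "the rate of loss to follow-up for the secondary objectives will be no more than 5" per cent. No loss is expected for the intra-operative primary outcome. The Allocation section prepares 33 blocks of 4, that is 132 allocations, at a 1:1 ratio.

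**The concern.** Table 2 gives two powers for one set of inputs: 80% in its first row and 1 in its last. Both cannot describe the same 125 patients. Taken at face value, the last row says the trial has practically no chance of missing a 15 psi difference, whereas a design with about 80% power misses it roughly one time in five. This is the protocol's only sample-size table, and the protocol is to be published, so the entry could be carried into the reading of a null primary result.

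For KOOS, the figure of 64 per group is a number of patients with data. The text sets it against the size of the trial as randomised, although the main KOOS endpoint is at 12 months, where the projected loss applies.

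**Working it through.** **Inputs.** Difference 15, SD 30, alpha 0.05, target power 80% and N = 125 come from Sample Size and Table 2. The 1:1 ratio comes from Allocation, and Student's t-test from Data Analysis. The number of sides is not stated, and two-sided is assumed. A one-sided test would need only 50 to 51 per arm, so a total of 125 points to a two-sided calculation.

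**Step 1: reproduce the 125.** The standardised difference is 15/30 = 0.5.

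- Normal approximation: n per arm = 2 × (1.960 + 0.842)² / 0.5² = 62.8, rounded up to 63, or 126 in total.
- t-test: 63.8 per arm, rounded up to 64, or 128 in total.

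The stated 125 lies within 3% of both, so the text reproduces to rounding.

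**Step 2: power obtained with 125 in total (62 and 63).**

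- Normal approximation: 0.5 / √(1/62 + 1/63) − 1.960 = 2.795 − 1.960 = 0.835, giving power 0.798.
- t-test: 0.792, a type II error of about 21%.

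**Step 3: look for a reading that gives 1.**

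| Reading of 125 | Power |
|---|---|
| Total, two-sided t-test | 0.792 |
| Total, one-sided (normal) | 0.875 |
| Per arm, two-sided t-test | 0.976 |
| One-sample test on 125 (normal) | 0.9999 |

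Only the one-sample test rounds to 1.00, and the trial is not a one-sample design.

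**Step 4: KOOS.** The standardised difference is 8/16 = 0.5, so the requirement is again 63 (normal) or 64 (t-test) per group. The protocol's figure of 64 reproduces. Applying the full 5% loss:

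| Randomised | With data (× 0.95) | Power, t-test | Power, normal |
|---|---|---|---|
| 125 | 118.75 | 77.1% | 77.8% |
| 128 | 121.6 | 78.1% | 78.7% |
| 132 | 125.4 | 79.3% | 79.9% |

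Without loss, the t-test powers are 79.2%, 80.1% and 81.4%. Keeping 64 per group after a 5% loss would take 128 / 0.95 = 134.7, or 135 randomised.

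**The case against.** The strongest reply is that the Table 2 entry is a display slip. A power of 0.79 or 0.80 printed without decimals becomes 1. The correct target stands in the first row of the same table and in the text, and nothing in the sample size, conduct or analysis depends on the last row. This is plausible, though the cause is an assumption. It limits the consequence, because a careful reader will see the 80% beside the 1, but it does not make the entry right.

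On KOOS, much of the defence stands. It is a secondary outcome, 64 is given as approximate, and 5% is an upper bound. There are 132 allocations where 32 blocks (128) would already cover 125. The protocol does not call the extra places a loss allowance, but they leave the gap under one point. At 10 points, the upper end of the stated minimal important change, power is 92% even with 125 randomised and 5% lost.

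A reader might go further and infer one of three things that the document does not support:

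- **That 125 for 80% power is itself wrong.** It is correct to rounding (Step 1).
- **That the KOOS power claim collapses after loss.** The shortfall is 2.9 points at worst.
- **That SD 16 cannot apply to a change score, so KOOS power is much lower.** This presumes that 16 is the SD at a single time point. The protocol quotes it alongside the minimal important change and does not settle which it is. If it is already an SD of change, the argument disappears. If it is a single-time SD, equal before and after surgery, the SD of change is 16 × √(2(1 − r)). That is larger than 16 for a pre/post correlation r below 0.5 and smaller above it, so power could move either way.

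**Conclusion.** The Table 2 entry is wrong. For 125 patients in total, the stated inputs give a power of 0.79 by t-test, or 0.80 by normal approximation, not 1. This rests on a two-sided 5% test and 1:1 allocation. No reading of 125 as a two-group comparison reaches 1. It is an error of reporting, not of design: the trial is sized as the text says.

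The KOOS omission is real but minor. At the full projected loss, power is about 77% from 125 randomised and about 79% from 132, against the 80% used in the calculation. These figures take the protocol's SD of 16 and difference of 8 points as given.

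**What to change.** 1. In Table 2, replace the obtained power of 1 with 0.79 (or 0.80, naming the normal approximation), and mark 125 as the total number of patients.
2. In the KOOS paragraph, state power after the projected loss at the actual recruitment target: about 77% if 125 are randomised, or about 79% if all 132 allocations are used.

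The sentence giving 125 patients for 80% power needs no change. The cost is two edited figures, slightly less favourable than those now shown. No patients are added, and the design and analysis stay as they are.
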